2.7.1.2 Adverse events of special interest / grouping of AEs

AEs of special interest (AESI) are defined in the latest version of the compound electronic Case Retrieval Strategy (eCRS). The classification reflects the safety topics of interest identified in the current version of the QGE031 Development Safety Profiling Plan and may be updated based on review of accumulating data. The number and percentage of participants with treatment emergent AEs of special interest will be summarized by risk category, PT and treatment. The search criteria in the latest eCRS corresponding the MedDRA version at the database lock will be used and reported in the CSR:

- Hypersensitivity reactions (including anaphylaxis)
- Cardiovascular and Cerebrovascular (CCV) events
- Neoplastic conditions
- Injection site reactions
- Serum Sickness
- Eosinophilic Conditions / Churg-Strauss Syndrome
- Parasitic (Helminthic) infections
- Thrombocytopenia

Injection Site Reactions

For treatment emergent injection site reactions (ISR), besides the overall summary table for AESI, number of participants with recurrence of ISR (single ISR, 2-3 ISRs, > 3 ISRs) will be summarized by treatment.

Adjudicated AEs

From the AESIs listed above, the following AEs will be adjudicated by the independent committee. The adjudicated events will be listed, and a summary table may be provided following the adjudication.

- Anaphylaxis
- Cardiovascular and Cerebrovascular (CCV) events
- Neoplastic conditions

In addition, summaries will be provided by subgroups of age and allergy status (mono-sensitized and poly-sensitized).

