Currently the standard of care for food allergy is limited to strict avoidance of the inciting food(s), rescue medication in case of unintentional exposure, and community wide interventions for schools (i.e., peanut free classrooms) and restaurants (i.e., ingredient alerts) (Jones and Burks 2017). Nevertheless, accidental exposures of food-sensitive individuals to the very antigen they are striving to avoid are frequent. For example, 58% of young children with clinical peanut hypersensitivity followed for up to 5 years experienced adverse reactions from accidental peanut exposure despite best efforts at allergen avoidance (Vander Leek et al 2000). Recently, a peanut oral immunotherapy (OIT) (Vickery et al 2018) was approved by FDA to mitigate allergic reactions during accidental exposure to peanuts (Jan-2020) and by EMA for the treatment of peanut allergy (Dec-2020). Yet this treatment is not fundamentally changing the unmet medical need in this space as it is only targeting one allergen; is indicated only for a subset of age groups and might not be suitable for all peanut allergic patients.

Due to rising prevalence (including allergy to multiple foods) (Sicherer and Sampson 2018), current limited therapeutic options and the lifelong disease burden in many, there is a recognized medical need to develop novel therapies for food allergy. Following the identification of IgE as a principal player in allergic diseases and the advent of monoclonal antibody (mAb) technology in the 1970s, mAbs to IgE were developed to the site on IgE that binds the FcεRI receptor (Baniyash et al 1988). These antibodies were identified based on their

ability to inhibit the IgE–FcεRI interaction and to block the activation of IgE sensitized cells. It was recognized that these antibodies would thereby prevent the initiation of the allergic cascade through both the FcεRI and FcεRII (CD23) pathways. Such antibodies are termed “non-triggering”; in contrast to conventional anti-IgE antibodies that cross-link cell bound IgE thus precipitating degranulation and even systemic anaphylaxis. Based on this strategy, the development of monoclonal anti-IgE treatment (TNX-901) was shown to be able to significantly increase the threshold of sensitivity to peanut antigen, as assessed by an oral food challenge (OFC), in a dose dependent manner, to levels that should translate into at least partial protection against most unintended ingestions of peanut (Leung et al 2003).

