Regarding Serious Adverse Events (SAEs), the incidence of SAEs was comparable between participants treated with ligelizumab and those receiving placebo in both asthma and CSU studies. There has been no dose dependency in SAEs observed among participants treated with different doses of ligelizumab (CQGE031B2201 in asthma and CQGE031C2201 in CSU).

Biologics can cause hypersensitivity reactions. Ligelizumab is in the same drug class as omalizumab, for which the risk and characteristics of anaphylaxis are well-characterized, and theoretically are applicable to the study drug. Investigators should therefore be alert to the occurrence of hypersensitivity events, including anaphylaxis, following the administration of ligelizumab and be familiar with the information and guidance provided in this protocol and in the Investigator Brochure.

IgE is an antibody that may have an adaptive role in immunity to parasitosis, particularly helminthic infections. Thus, blocking the interaction of IgE and its receptors with ligelizumab may alter immunologic responsiveness to parasites. Bearing this in mind, monitoring for the occurrence of infection and response to therapy is recommended for participants at high risk of geohelminth infection who receive ligelizumab. Insufficient data are available to determine the length of monitoring required for geohelminth infections after stopping ligelizumab. However, it is expected that ligelizumab will not interfere with a polyclonal reaction triggered by exposure to parasites. The resulting increase of IgE production would decrease, through target-mediated disposition, the half-life of ligelizumab hence restoring normal IgE levels more rapidly.

Therefore, based on the cumulative data available across all clinical studies in different participant populations for ligelizumab, the current evidence demonstrates that ligelizumab is safe and well tolerated and thus appropriate for further development.

The non-clinical safety evaluation for ligelizumab supports a clinical treatment of children down to the age of 2 years: [REDACTED]

[REDACTED] No new or unexpected safety signals were identified in the CQGE031C2201 (CSU dose-ranging) study in adults.

This study is placebo-controlled design and approximately one-third of participants will receive placebo by randomization (Section 4.3), however, the participants who are initially allocated to placebo will be switched to the active treatment (ligelizumab 120 or 240 mg SCq4w) at Week

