### **Assessment of anaphylactic events**

An adjudication committee (AC) will be put in place to determine whether cases of hypersensitivity identified through a search algorithm based on the Standardized MedDRA Queries may represent cases of anaphylaxis. Further details regarding the AC will be documented in an AC charter.

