2.7.1 Adverse events (AEs)

Unless otherwise specified, summaries will include treatment-emergent adverse events (TEAEs) only. Treatment emergent adverse events are defined as events started after the first dose of study treatment and within 16 weeks after the last study treatment, or events present prior to the first dose of study treatment but increased in severity based on preferred term within 16 weeks after the last study treatment. All events that the investigator classifies as reactions associated to the DBPCFC or SPT will not be included in reporting of treatment-emergent AEs and may be reported separately. The number and percentage (with exact binomial 95% CIs) of participants with TEAEs will be summarized in the following ways:

- by treatment, primary system organ class and preferred term.
- by treatment, primary system organ class, preferred term and maximum severity.
- by treatment, Standardized MedDRA Query (SMQ) and preferred term.

Separate summaries will be provided for study treatment-related adverse events, death, serious adverse events, other significant adverse events leading to discontinuation and TEAEs with potential cause of accidental exposure or ingestion. If a participant reported more than one AE with the same preferred term, the AE with the greatest severity will be presented. If a participant reported more than one AE within the same primary system organ class, the participant will be counted only once with the greatest severity at the system organ class level, where applicable.

For the legal requirements of ClinicalTrials.gov and EudraCT, two required tables on TEAEs which are not SAEs with an incidence greater than a certain threshold based on the final database and on TESAEs and SAEs suspected to be related to study treatment will be provided by system organ class and PT on the safety set population.

If for a same patient, several consecutive AEs (irrespective of study treatment causality, seriousness and severity) occurred with the same SOC and PT:

- a. a single occurrence will be counted if there is ≤ 1 day gap between the end date of the preceding AE and the start date of the consecutive AE
- b. more than one occurrence will be counted if there is > 1 day gap between the end date of the preceding AE and the start date of the consecutive AE

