Safety	Treatment-emergent Adverse Events of Special Interest (AESI), by standardized MedDRA term (plus respective listing)
Safety	Number of AEs (n, %)
Safety	Newly occurring or worsening chemistry and hematology abnormalities (plus respective listing)
Safety	Newly occurring or worsening vital sign abnormalities (plus respective listing)
Safety	Adverse events for screen failures
Safety	Number of Subjects with Adjudicated Anaphylaxis Events (Safety Set) (plus respective listing)
Safety	Number of Subjects with Adjudicated CCV Events (Safety Set) (plus respective listing)
Safety	Number of Subjects with Adjudicated Neoplastic Events (Safety Set) (plus respective listing)
Safety	Number of AEs requiring Epinephrine treatment (n, %)
Disposition	Participant Disposition at Treatment Period (Randomized Set)
Set	Analysis Sets (Randomized Set)
Baseline	Subject Demographics (Randomized Set)
Baseline	Subject Baseline Characteristics (Randomized Set)

In addition, the following analyses will be presented.

DMC analyses:

The DMC will assess, at defined intervals, the progress of a clinical trial, safety data, and critical efficacy variables and recommend to the sponsor whether to continue, modify, or terminate a trial, as defined in the DMC charter. Analysis of selected efficacy variables will be provided only for the purpose of helping for safety evaluation. Such assessments do not inflate the Type I error for the primary efficacy hypothesis testing and thus no adjustment for multiplicity is required.

3 Sample size calculation

A total sample size of approximately 486 randomized participants is originally planned to achieve sufficient power for the primary and key secondary endpoints, and it provides adequate precision in estimating AE rates in this study. Due to the halt of recruitment, the sample size is now 211. This reduced sample size provides sufficient power for the primary endpoint.

Participants will receive one of three treatments (ligelizumab 240mg SCq4w, ligelizumab 120mg SCq4w, or placebo SCq4w) and will be randomized into five treatment arms with a ratio 2:2:2:2:1. At the start of the study, recruitment was restricted to participants 12-55 years old. Due to the recruitment halt, no other age groups were recruited.

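### In the two placebo-controlled safety pools, the hypersensitivity AESI and adjudicated-anaphylaxis rows mix accidental food reactions with possible drug reactions, which biases the active-placebo contrast in those rows toward no harm

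*SAP*

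**What the plan says.** SAP 2.7.1.2 defines the adverse events of special interest (AESI) and their table: "The number and percentage of participants with treatment emergent AEs of special interest will be summarized by risk category, PT and treatment". The first category listed is "Hypersensitivity reactions (including anaphylaxis". No split by cause is specified.

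SAP 2.7.1 excludes from treatment-emergent events only the reactions that the investigator attributes to the food challenge or the skin prick test. The same section plans separate general summaries, among them study treatment-related events and "TEAEs with potential cause of accidental exposure or ingestion". Neither is said to be applied within the AESI or adjudicated outputs.

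Protocol 8.4.4 gives the anaphylaxis committee's task as "to determine whether cases of hypersensitivity identified through a search algorithm based on the Standardized MedDRA Queries may represent cases of anaphylaxis". It does not mention cause and leaves further detail to a charter. SAP Table 2-2 (section 2.13) lists "Number of Subjects with Adjudicated Anaphylaxis Events (Safety Set) (plus respective listing"; SAP 2.7.1.2 makes the adjudicated summary table optional.

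SAP 2.1.1.1 sets three safety pools: to Week 8 (each dose against three placebo arms combined), to Week 16 (each dose against the 16-week placebo arm), and the entire study (240 mg against 120 mg, with no placebo column).

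**The concern.** Protocol 4.5 places ligelizumab in the same class as omalizumab, "for which the risk and characteristics of anaphylaxis are well-characterized, and theoretically are applicable to the study drug". The hypersensitivity category is the output built to show that risk. Protocol 1.2 states the treatment's aim as protection against allergic reactions after accidental exposure to food. Both kinds of event produce the same hypersensitivity and anaphylaxis terms.

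A single row therefore adds events the drug may cause to events it is meant to prevent. If the drug works, the active arms lose some food reactions, and that loss offsets any drug reactions they gain. The offset needs a placebo column, so it concerns the Week 8 and Week 16 pools and not the entire-study pool.

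**Working it through.** **Check on the plan's own safety figure.** SAP Table 3-3 gives (0.1%, 3.5%) for a 1% event rate in 211 participants. The exact Clopper-Pearson interval is 0.13% to 3.46%, which agrees. The point disputes none of the plan's numbers.

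**Inputs**
- Arm sizes: SAP 3.1 gives about 46 per dose and 23 on placebo. For the Week 8 pool, five of the nine randomisation shares are placebo: 211 × 5/9 = 117.
- Background rate: the only figure in the documents is Protocol 1.1, "58% of young children with clinical peanut hypersensitivity followed for up to 5 years experienced adverse reactions from accidental peanut exposure". Assuming a constant hazard over a full 5 years (260 weeks), hazard = -ln(0.42)/260 = 0.00334 per week.
- Assumed, not in the documents: relative reduction in food reactions on drug, e = 40% to 80%; drug-reaction risk, d = 4% on active and 0% on placebo; no other hypersensitivity.

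**Accidental-reaction risk on placebo (a)**
- 8 weeks: 1 - 0.42^(8/260) = 2.6%
- 16 weeks: 1 - 0.42^(16/260) = 5.2%

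**Expected contrast.** Pooled active risk = 1 - (1 - a(1 - e))(1 - d); placebo risk = a. The two are equal when d = 1 - (1 - a)/(1 - a(1 - e)).
- 16 weeks: break-even d is about 2.1% (e = 40%) to 4.2% (e = 80%).
- 8 weeks: about 1.1% to 2.1%.

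A drug-reaction risk up to the break-even value gives an expected difference of zero or below in the pooled row. Larger risks still show as harm.

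**Chance that a trial shows active % at or below placebo %, d = 4%** (exact binomial enumeration)

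| Row | Week 16, 46 v 23 | Week 8, 46 v 117 |
|---|---|---|
| Pooled, e = 40% | 43% | 22% |
| Pooled, e = 80% | 57% | 30% |
| Pooled, no protective effect (e = 0) | 32% | 15% |
| Perfectly separated, no other hypersensitivity | 0.96^46 = 15% | 0.96^46 = 15% |

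The part due to opposing effects is the excess over the third line: 43 - 32 = 11 to 57 - 32 = 25 points at 16 weeks, and 22 - 15 = 7 to 30 - 15 = 15 points at 8 weeks.

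**Sensitivity**
- Halving the background risk gives 33-40% (Week 16) and 16-19% (Week 8).
- With d = 2%, the Week 8 pooled row gives 41-55%, and a separated row gives 0.98^46 = 39%. At low drug-reaction rates, small numbers limit the separated row as well.

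**The case against.** The strongest reply is that the plan already offers a view by cause. SAP 2.7.1 summarises treatment-related events and accidental-exposure events separately. Protocol 10.1.1 requires a causality assessment for every adverse event and has investigators ask about hypersensitivity after the challenge, the injection and accidental ingestion. Table 2-2 adds listings for accidental-exposure events, AESIs and adjudicated anaphylaxis. Anaphylaxis counts will be small, so case review is feasible. This stands: a reader could infer that the class risk would be hidden from the safety evaluation, and the documents do not support that. What remains is that none of these outputs gives a between-arm comparison of hypersensitivity with food reactions set apart. The treatment-related table also misses a drug reaction that the investigator did not suspect.

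Second, one could infer that adjudication ignores cause. That does not follow. The charter and the electronic case retrieval strategy that defines the AESIs are not available, and either may record it. The SAP specifies no output that uses such a field.

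Third, the size is easy to overread. The whole 43-57% should not be put down to masking, since 32% arises with no protective effect. Nor is the 85% chance of at least one active case in a separated row (1 - 0.96^46) a fair contrast, because on that measure the pooled row scores 91-96%. The 58% concerns young children and any reaction, whereas the trial recruited ages 12-55, and anaphylaxis is a much narrower outcome.

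Fourth, a row defined by recorded cause rests on investigator attribution. That is a sound reason not to let it replace the randomised all-events comparison.

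**Conclusion.** The concern holds for two outputs in two pools. In the Week 8 and Week 16 placebo-controlled pools, the hypersensitivity AESI row and the adjudicated-anaphylaxis count are not planned by cause, and their active-placebo contrast is biased toward no harm if the drug prevents food reactions. The direction follows from the mechanism. The amount does not follow from the documents: the 11 to 25 points (Week 16) and 7 to 15 points (Week 8) depend on the assumed hazard, reduction and drug-reaction rate, and on the match between young children and this population. They illustrate any hypersensitivity reaction and should not be applied to adjudicated anaphylaxis.

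The signal is obscured in these tables but can be recovered by hand from others. This is a cheap and worthwhile improvement to presentation, not a failure of the safety plan.

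**What to change.** In SAP 2.7.1.2, for the Week 8 and Week 16 pools, present the hypersensitivity AESI category and adjudicated anaphylaxis in three rows:

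1. all events, kept as the randomised comparison;
2. events with accidental food exposure recorded as potential cause;
3. events without it.

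State that attribution is made before unblinding, and that rows 2 and 3 are read beside row 1 when drug hypersensitivity is assessed.

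The cost is SAP wording and one extra breakdown of planned tables. No new data should be needed, because SAP 2.7.1 and Table 2-2 already use the recorded accidental-exposure cause. The drawbacks are small cells and reliance on the blinded investigator's record. Unrecognised food exposures stay in row 3, so the bias there is reduced and not removed.

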2.7.2 Deaths

The number of deaths resulting from TEAEs will be summarized by SOC and PT. All the deaths in the clinical database including those occurring during screening will be listed.

2.7.3 Laboratory data

The descriptive summary statistics (mean (95% CI), median, first and third quartiles, minimum and maximum) for change from baseline to each study visit and maximum/minimum value will be presented. These descriptive summaries will be presented by test group, laboratory test and treatment group. Change from baseline will only be summarized for participants with both baseline and post baseline values for quantitative parameters, and the maximum/minimum value could come from post-baseline scheduled, unscheduled or premature discontinuation visits. For categorical parameters, frequencies by categories at each visit will be summarized.

The laboratory values below Lower Level of Quantification (LLOQ) or above Upper Level of Quantification (ULOQ) will be imputed as LLOQ or ULOQ in the summary tables, respectively. The numerical part of the reported result will be treated as the actual LLOQ or ULOQ. These laboratory values will be displayed in listings using the standard unit with the reported sign (“<” or “>”).

For selected laboratory parameters, abnormalities occurring at any time-point from scheduled, unscheduled and premature discontinuation visits considering all post-baseline on-treatment data will be summarized. Where normal ranges are available, abnormalities in laboratory data may be listed by, participant, and visit/time.

The number of participants with worsening abnormality during the study will be summarized by treatment. A case is considered as worsening abnormality if the value at baseline and at least one post-baseline value during the study is worse than baseline.

2.7.4 Other safety data

2.7.4.1 ECG

Summary statistics (absolute values and change from baseline) for all ECG parameters will be provided by treatment and time point; Participants with notable abnormalities in ECG data will be listed by treatment group and visit/time. The following will be considered as notable values for adults: QT > 500 msec; QTcF > 450 msec (males), QTcF > 460 msec (females); PR > 250 msec. The following will be considered as notable ECG values for adolescents: QTcF >450 msec (males), QTcF >460 msec (females); PR >250 msec.

For ECG parameters, the number and percentage of patients with worsening abnormalities occurring post-baseline will be summarized using shift table by treatment group. The definition worsening is the same as laboratory values.

2.7.4.2 Vital signs

[figure not shown]
Summary statistics will be provided by vital sign, treatment group and visit/time as appropriate. Change from baseline will only be summarized for participants with both baseline and post-baseline values. Participants with notable vital signs as defined below will be listed.

[figure not shown]
For adults:

[figure not shown]
- Hypertension (systolic blood pressure of ≥ 140 mmHg and/or diastolic blood pressure of ≥ 90 mmHg) or hypotension (systolic blood pressure of < 90 mmHg and/or diastolic blood pressure of < 60 mmHg)
- Pulse rate below 60 bpm (bradycardia) or above 100 bpm (tachycardia)

For adolescents:

See [Section 5.3](#) for upper and lower limits for vital signs.

2.10 Patient-reported outcomes

2.10.1 Patient-reported outcome assessments

PRO data will be analyzed in accordance with the secondary endpoint described in [Section 1.2](#). The following measures are being administered based on age group and responder type:

- FAQLQ-CF: Food Allergy Quality of Life Questionnaire – Child Form (completed by children aged 8-12)
- FAIM-CF: Food Allergy Independent Measure – Child Form (completed by children aged 8-12)
- FAQLQ-TF: Food Allergy Quality of Life Questionnaire – Teenager Form (completed by adolescents aged 13-17)
- FAIM-TF: Food Allergy Independent Measure – Teenager Form (completed by adolescents aged 13-17)
- FAQLQ-AF: Food Allergy Quality of Life Questionnaire – Adult Form (completed by adults aged 18-55)
- FAIM-AF: Food Allergy Independent Measure – Adult Form (completed by adults aged 18-55)
- FAQLQ-PF: Food Allergy Quality of Life Questionnaire – Parental Form (completed by same parent/caregiver of children aged 0-12)
- FAQL-PB: Food Allergy Quality of Life – Parental Burden Questionnaire (completed by same parent/caregiver of children aged 0-17)

- SF-36v2 Acute Version – Medical Outcomes Study 36-Item Short Form Version 2 Acute Version (recall period is past week) (completed by adults aged 18-55)

Table 2-1 Administration of questionnaires according to participant age.

Age Group / Respondent Type	Questionnaire	Day 1 Randomization	Week 12 (10 Days Before D1 OFC)	Week 12 (3 Days After D2 OFC)	Week 52 (10 Days Before D1 OFC)	Week 52 (3 Days After D2 OFC)
Children aged 12	FAQLQ-CF	x	x	x	x	x
	FAIM-CF	x	x	x	x	x
Teenagers aged 13-17	FAQLQ-TF	x	x	x	x	x
	FAIM-TF	x	x	x	x	x
Adults aged 18+	FAQLQ-AF	x	x	x	x	x
	FAIM-AF	x	x	x	x	x
	SF-36v2	x		x		x
Parents/ Caregivers of Children aged 13-17	FAQL-PB	x	x	x	x	x
Parents/ Caregivers of Children aged 12	FAQLQ-PF	x	x	x	x	x

The Food Allergy Quality of Life Questionnaire (FAQLQ) is a self-reported instrument intended to assess the effect of food allergy on the participant's health-related quality of life (HRQoL). The FAQLQ-CF (aged 8-12) (Flokstra – de Blok, DunnGalvin et al. 2009), FAQLQ-TF (aged 13-17) (Flokstra – de Blok, DunnGalvin et al. 2008) and FAQLQ-AF (≥ 18 years of age) (Flokstra-de Blok, van der Meulen et al. 2009) are self-administered, validated food allergy-specific HRQoL questionnaires. The FAQLQ-PF is completed by parents of children aged 0 - 12 with food allergy (DunnGalvin, de BlokFlokstra et al. 2008).

Scoring of PRO Instruments

The number of items and domains varies by FAQLQ instrument administered. Each question is scored on a 7-point scale (coded as 1-7 in analysis, with a higher level indicating greater impairment in HRQoL). The total score is the arithmetic average of all completed items. Domain scores are calculated similarly for each form as following:

FAQLQ-CF: Emotional impact (EI) (item no. 19-24), Allergen avoidance (AA) (item no. 4, 6-10, 15), Risk of accidental exposure (RAE) (item no. 11, 13, 14, 16, 17), Dietary restriction (DR) (item no. 1-3, 5, 12, 18)

FAQLQ-TF: Emotional impact (EI) (item no. 5, 12, 19-23), Allergen avoidance and dietary restrictions (AADR) (item no. 1-4, 6-10, 16), Risk of accidental exposure (RAE) (item no. 11, 13-15, 17, 18)

FAQLQ-AF: Emotional impact (EI) (item no. 5, 24-29), Allergen avoidance and dietary restrictions (AADR) (item no. 1-4, 6, 8-12, 20), Risk of Accidental Exposure (RAE) (item no. 7, 13-18, 21), Food allergy related health (FAH) (item no. 19, 22, 23)

FAQLQ-PF: Emotional impact (EI) (item no. 2, 6, 7, 9-11, 23-28, 30), Food anxiety (FA) (item no. 1, 4, 5, 16, 17, 20, 21, 29), Social and dietary limitations (SDL) (item no. 3, 8, 12-15, 18, 19, 22).

If more than one item in any domain is missing, a domain score should not be calculated for that case. A total score can still be calculated if 20% or fewer of the items are missing.

The FAIM reflects the participant's perceived food allergy severity and food allergy-related risk ([van der Velde, Flokstra-de Blok et al. 2010](#)). Each question is scored on a 7-point scale (coded as 1-7 in analysis, with a greater score indicating a higher level of perceived risk or chance of adverse events occurring). The total score is the arithmetic average of all completed items. If less than 80% of the items within the score are complete, it will not be calculated. Questions 4 and 5 (effectively managing a reaction, receiving sufficient help from others) must be reverse coded.

A threshold of 0.45 points has been suggested and used as a minimal important difference (MID) to interpret clinical relevance ([Dunn Galvin, Cullinane et al. 2010](#)). For FAQLQ and FAIM forms, the 0.45 threshold will be used to interpret the clinical relevance of group-level differences and changes, in addition to within-patient changes.

The FAQL-PB is a self-administered, disease-specific instrument developed to measure the effect of pediatric food allergy on HRQoL for caregivers ([Cohen, Noone et al. 2004](#)). The instrument includes 17 items (assessing social, dietary and emotional impacts) on the impact of having a child with food allergy on the parents themselves using a 7-point Likert scale ranging from 0 (not limited/troubled) to 6 (extremely limited/troubled). The total score is the arithmetic average of all completed items.

The SF-36v2® Health Survey is a 36-item instrument that measures generic health-related quality of life. It is designed for use in surveys of general and specific populations, health policy evaluations and clinical practice and research. Two forms of this instrument are available and this study will use the one-week recall (acute) form. The SF-36v2 contains 8 scales and 2 component summary indices evaluating physical, social and emotional functioning in addition to general health perceptions and mental health.. Responses to items allow for direct calculation of scale scores, while the physical component summary (PCS) and mental component summary (MCS) scores are computed from weighted scale scores. The SF-36v2 scale and composite scores can be converted to a T-score metric, allowing for norm-based scores derived from responses to a 2009 survey conducted by QualityMetric.⁴ For all scales and summary measures, higher scores indicate better health outcomes.

The SF-6Dv2 will be derived from the SF-36v2 for health economic evaluations ([Brazier, Mulhern et al. 2020](#)). The SF-6Dv2 captures the impact of diseases and conditions on social activities and depression/nervousness. The SF-6Dv2 questionnaire uses a standardized health state descriptive system consisting of 6 dimensions, including social limitations, which was deemed essential to cover in food allergy. All dimensions are expressed over 5 levels, except for pain, which uses 6 levels, allowing for the description of 18,750 different health states. Health states are described using a combination of 6 digits each expressing the level for a dimension. For example, state "111111" indicates perfect health and state "555655" indicates the worst possible health status. The resulting SF-6Dv2 index, scored from 0.0 (worst health

state) to 1.0 (best health state), can be used in the assessment of the quality adjusted life years (QALYs) and the cost-effectiveness of various health care interventions.

